16.4.5. Efficacy Endpoints Analyses

Annualized Relapse Rate

Relapses will be summarized over the follow-up period in Study 205MS303. For subjects in Study 205MS301 and Study 205MS303 ITT population, relapses may be summarized over the combined study period (Studies 205MS301 and 205MS303).

A negative binomial regression model will be used to estimate the adjusted ARR.

Proportion of Subjects with a Relapse

The proportion of subjects relapsed will be estimated using a Kaplan-Meier curve.

Disability Progression

Sustained disability progression is defined as at least a 1.0 point increase on the EDSS from baseline EDSS ≥ 1.0 that is sustained for 24 weeks, or at least a 1.5 point increase on the EDSS from baseline EDSS < 1.0 that is sustained for 24 weeks. The proportion of subjects with progression will be summarized using a Kaplan-Meier curve. In addition, summary statistics for EDSS and for the change from baseline in EDSS will be presented by visit, and for subjects who participated in Study 205MS301, by previous treatment group.

MSFC

Changes in the MSFC z-score will be summarized by study visit, and for subjects who participated in Study 205MS301, by previous treatment group. For subjects in Study 205MS301 and Study 205MS303 ITT population, MSFC z-score may be summarized over the combined study period (Studies 205MS301 and 205MS303). Details on the calculations of the z-score for each component will be described in the statistical analysis plan.

SDMT

Changes in the SDMT scores will be summarized by study visit and by previous treatment group in Study 205MS301. Change in the SDMT scores over the combined study period (Studies 205MS301 and 205MS303) will be calculated using the Study 205MS301 baseline visit

CONFIDENTIAL

The information contained herein may not be used, disclosed, or published without the written consent of Biogen MA Inc.

as baseline. Change in the SDMT score over the Study 205MS303 study period will be calculated using the last SDMT measurement in Study 205MS301 as baseline.

PASAT 3

Changes in the PASAT 3 scores will be summarized by study visit and by previous treatment group in Study 205MS301. Change in the PASAT 3 scores over the combined study period (Studies 205MS301 and 205MS303) will be calculated using the Study 205MS301 baseline visit as baseline. Change in the PASAT 3 score over the Study 205MS303 study period will be calculated using the Week 0/baseline visit as baseline.

MRI Endpoints

MRI endpoints will be summarized with descriptive statistics both as a continuous variable and categorically. Over time summaries and summaries by previous treatment group (Avonex or DAC HYP 150 mg) may also be provided. A negative binomial regression model will be used for the analysis of new or newly enlarging T2 lesions. The change in volume of lesions will be analyzed using an analysis of covariance.

Quality of Life Outcomes

Actual scores and change from baseline in quality of life endpoints will be summarized by visit.

Pharmacokinetics

The population for DAC HYP concentration analyses will include all subjects who received at least 1 dose of study medication and who have at least 1 sample available for analysis.

Serum concentration levels will be summarized with descriptive statistics by visit.

Antigenicity/Immunogenicity Data

Immunogenicity (i.e., ADAs to DAC HYP) will be assessed on subjects. Positive samples will be further tested for neutralizing antibodies to DAC HYP using a specific NAb assay. Results will be tabulated by time period and overall.

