16.4.2. General Methods of Analysis

Summary statistics will be presented. For continuous endpoints, summary statistics will generally include the number of subjects with data, mean, standard deviation, median, and range. Categorical endpoints will include the number of subjects with data and the percentage in each category.

Analyses will generally be descriptive in nature and will focus on data collected during Study 205MS303 only. However, for relevant efficacy analyses, the data may be summarized by previous treatment group (Avonex or DAC HYP). Also, statistical comparisons may be made between efficacy in Study 205MS301 and efficacy in Study 205MS303 among subjects previously randomized to Avonex in Study 205MS301.

All statistical tests will be 2-sided with an overall Type I error of 5%. Adjustments for multiple comparisons will not be considered.

CONFIDENTIAL

The information contained herein may not be used, disclosed, or published without the written consent of Biogen MA Inc.

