16.4.4. Other Safety Endpoint Analyses

Unless otherwise specified, the baseline measurement for safety assessments such as laboratory values and vital signs was the measurement acquired on the day of the first receipt of DAC HYP. The first receipt of dosing of DAC HYP could be either Study 205MS303 (for subjects who received Avonex in Study 205MS301) or the parent studies (i.e., Study 205MS301, Study 205MS203, or Study 205MS302) for all other subjects.

Laboratory Data

Changes in laboratory values will be summarized using shift tables. Shift tables will include hematology, LFTs, kidney function tests, electrolytes, and other blood chemistry tests. Shifts will be presented from baseline of DAC HYP treatment (the last measurement acquired before or on the day of the first receipt of DAC HYP, e.g., Study 205MS303 baseline for subjects randomized to Avonex in Study 205MS301 and Study 205MS301 baseline for subjects randomized to DAC HYP 150 mg in Study 205MS301). Summaries of worst post-baseline laboratory values by clinically relevant categories may also be presented for selected parameters of interest by treatment group. For example, for LFT (alkaline phosphatase, ALT, AST, GGT, and total bilirubin), categories may be defined based on cutoff values relative to the ULN.

Vital Signs

Vital signs collected will be examined to determine the incidence of clinically relevant abnormalities. These abnormalities are described in [Table 8](#). For the purpose of the shifts from baseline, the baseline evaluation at the start of DAC HYP treatment will be used.

For each vital sign, the number of subjects evaluated and the number and percentage of subjects with the defined abnormality at any time post dosing will be presented by treatment group.

CONFIDENTIAL

The information contained herein may not be used, disclosed, or published without the written consent of Biogen MA Inc.

Table 8: Criteria to Determine Clinically Relevant Abnormalities in Vital Signs

Vital Sign	Criteria for Abnormalities
Temperature	>38°C or an increase from baseline of $\geq 1^\circ\text{C}$
Pulse	>120 beats per minute (bpm) or an increase from baseline of 20 bpm <50 bpm or a decrease from baseline of >20 bpm
Systolic Blood Pressure	>180 mmHg or an increase from baseline of >40 mmHg <90 mmHg or a decrease from baseline of >30 mmHg
Diastolic Blood Pressure	>105 mmHg or an increase from baseline of >30 mmHg <50 mmHg or a decrease from baseline of >20 mmHg

Physical Examination

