6.1.2. Secondary Objectives

Secondary objectives of this study in this study population are as follows:

- To describe MS-related outcomes, including MS relapse, disability progression, MS lesion formation, and patient-reported impact of MS, following long-term treatment with DAC HYP
- To assess the long-term immunogenicity of DAC HYP administered by PFS
- To assess the safety, tolerability, and efficacy of switching to DAC HYP in subjects previously on long-term treatment with interferon β -1a in Study 205MS301

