Serum concentration levels will be summarized with descriptive statistics by treatment group and visit. PK data from this study will be used in combination with PK data from other DAC HYP trials for population PK analysis. Details on the analysis will be described in a separate population PK-PD analysis plan.

Pharmacodynamics

Summary statistics for PD variables will be summarized by treatment group and study visit.

Antigenicity/Immunogenicity Data

Immunogenicity (i.e., anti-DAC antibodies) will be assessed on all subjects. Positive samples will be further tested for neutralizing anti-DAC antibodies using a specific neutralizing antibody (NAb) assay. Results will be tabulated by time period, treatment group, and overall.

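### Serum concentrations and anti-drug antibodies are summarised with first-exposed and previously exposed subjects pooled, so the Week 0 (and possibly Week 144) trough means and the overall antibody figure cannot be read by exposure history

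*Protocol*

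**What the plan says.** In the current text of Section 16.4.5, the concentration population is "all subjects who received at least 1 dose of study medication and who have at least 1 sample available for analysis", and "Serum concentration levels will be summarized with descriptive statistics by visit". For antibodies to DAC HYP, including neutralising antibodies, "Results will be tabulated by time period and overall". Neither summary is divided by prior treatment or by parent study.

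Version 1 of the same section divided both: "Serum concentration levels will be summarized with descriptive statistics by treatment group and visit", and for antibodies "Results will be tabulated by time period, treatment group, and overall". The division is absent from Version 2 and from the current text.

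Elsewhere in the current Section 16.4.5, EDSS, MSFC, SDMT and PASAT 3 are summarised by previous treatment group in 205MS301. Section 16.4.2 adds a general option: "for relevant efficacy analyses, the data may be summarized by previous treatment group (Avonex or DAC HYP"). Section 16.4.4 says that, unless otherwise specified, the baseline for safety assessments such as laboratory values and vital signs "was the measurement acquired on the day of the first receipt of DAC HYP". For previously exposed subjects that day falls in a parent study.

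The related secondary objective (Version 2, Section 6.1.2) is "To assess the long-term immunogenicity of DAC HYP administered by PFS". The opening part of the current version is not in the file, so the objectives, endpoints and sampling tables used here are those of Version 2.

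**The concern.** Three groups with different exposure histories share one column. Former Avonex subjects have no DAC HYP on board at Week 0. Roll-overs from the DAC HYP arm of 205MS301 may be at trough, or partly washed out. Subjects from 205MS203 and 205MS302 join at Week 144, up to 6 months after their last parent-study dose. A single mean at a visit where these groups differ describes none of them. The rise that follows Week 0 comes from the switchers, yet the table shows it for everyone.

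For antibodies, only the switchers can show new formation from first exposure within this study. Previously exposed subjects may enter already positive, or may have passed through first exposure without seroconverting. An overall figure across all of them cannot show how much antibody formation belongs to 205MS303. Long-term immunogenicity and switching from interferon are both stated secondary objectives, so this is the information the tables are meant to provide.

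**Working it through.** The plan gives no figure to reproduce here: Section 16.6 has no sample size calculation, and no trough level or antibody rate for 205MS303 is stated.

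**Inputs from the protocol**
- About 1200 subjects from 205MS301 and about 400 from 205MS203 and 205MS302, in total 1200 + 400 = 1600 (Version 2, Section 7.1).
- 1:1 randomisation in 205MS301 (Version 2, Section 5.1).
- One injection every 4 weeks (Section 11.1).
- Concentration and antibody samples at Weeks 0, 12, 24 and 48 (Version 2, Table 1), and at Week 144 for both continuing subjects (Table 2) and new entrants (Table 3). Week 0 is pre-dose.
- Gaps of up to 6 months: from completing 205MS301 to baseline (Version 1, Table 1 footnote), and from last parent-study dose to the Week 144 Entry Visit (Version 2, Table 3 footnote).

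**Assumptions, not in the protocol**
- Half of the 205MS301 roll-overs are former Avonex subjects.
- One-compartment elimination with a half-life of 14, 21 or 28 days.
- Gap since last parent-study dose of 28 days (no interruption), 84 or 182 days.

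**Concentrations, as a fraction of steady-state trough.** With half-life h in days, let r = 2^(−28/h).
- Prior Avonex after k doses: 1 − r^k.
- Prior DAC HYP with gap g: 1 − r^k + c·r^k, where c = 2^(−(g − 28)/h).
- Pooled mean: the average of the two.
- Example: h = 28 gives r = 0.5. At Week 12 (k = 3), prior Avonex is 1 − 0.125 = 0.875. With no interruption prior DAC HYP is 1.000, and the pooled mean is 0.938.

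Ranges over the three half-lives:

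| Gap | Week 0 prior Avonex | Week 0 prior DAC HYP | Week 0 pooled | Week 12 prior Avonex | Week 12 prior DAC HYP | Week 12 pooled |
|---|---|---|---|---|---|---|
| 28 days | 0 | 1.000 | 0.500 | 0.875–0.984 | 1.000 | 0.938–0.992 |
| 84 days | 0 | 0.062–0.250 | 0.031–0.125 | 0.875–0.984 | 0.906–0.985 | 0.891–0.985 |
| 182 days | 0 | 0.000–0.022 | 0.000–0.011 | 0.875–0.984 | 0.878–0.984 | 0.876–0.984 |

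By Week 24 prior Avonex is at 0.984–1.000, and the pooled mean is within about 1% of both groups. With no interruption, the Week 0 pooled fraction is 1 minus the switcher share: 0.40–0.60 for a share of 60–40%.

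**Week 144.** Take the planned numbers with no dropout, continuing subjects at 1 and entrants at c. The pooled mean is (1200 × 1 + 400 × c)/1600. This is 1.00 if no entrant had a gap (c = 1) and 0.75 if all were washed out (c = 0).

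**Antibodies.** Assume 600 prior Avonex and 600 prior DAC HYP subjects, carried-in positivity p in the latter, new positivity q in prior Avonex, and 1% new positivity in prior DAC HYP subjects negative at entry.
- Any positive, overall: [600q + 600(p + (1 − p) × 0.01)]/1200.
- Newly positive among those negative at entry: [600q + 600(1 − p) × 0.01]/[600 + 600(1 − p)].
- Example: p = 5%, q = 10%. Any positive is (60 + 35.7)/1200 = 7.98%. Newly positive is (60 + 5.7)/1170 = 5.62%. Carried-in share of all positives is 30/95.7 = 31%.

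| p | Any positive, q = 5–20% | Newly positive, q = 5–20% | Carried-in share of positives |
|---|---|---|---|
| 0% | 3.00–10.50% | 3.00–10.50% | 0% |
| 2% | 3.99–11.49% | 3.02–10.60% | 25–9% |
| 5% | 5.48–12.98% | 3.05–10.74% | 46–19% |
| 10% | 7.95–15.45% | 3.11–11.00% | 63–32% |

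These rates only show how the two counts diverge. They do not estimate what happened in the trial.

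**The case against.** Much of the case on the other side stands.

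- A reader might infer that antibodies acquired in a parent study will be counted as 205MS303 incidence. The protocol does not say so. It gives no counting rule for entry-positive subjects, such a rule may sit in an analysis plan that is not shown, and tabulation by period could display Week 0 positives separately. If the Section 16.4.4 baseline extends to immunogenicity, which Section 13.1 lists as a safety assessment, a count from first-ever DAC HYP would be intended.
- A reader might infer that early trough means in general describe nobody, or that the table will show false accumulation across the study. The arithmetic does not support that: the mixing matters at Week 0 and possibly Week 144, and with a long gap the Week 0 contrast disappears too. Section 16.4.2 also provides for the median and range, so zeros at Week 0 would be visible.
- The Section 16.4.2 option permits a split by previous treatment, and these paragraphs sit under the efficacy heading.
- The Version 1 wording is superseded. Its removal shows a change, not in itself a mistake.
- All of this is descriptive; no test or threshold depends on it.

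What does not stand is the view that this is only detail left for later. The protocol states how each summary is to be broken down and omits prior exposure, while naming it for four other outcomes in the same section. The Section 16.4.2 option is discretionary, limited to relevant efficacy analyses and to two groups, and does not cover the Week 144 entrants or antibody status at entry. Section 16.4.2 also focuses on data collected in 205MS303, whereas the Section 16.4.4 baseline can start in the parent study. Applied to antibodies, these give different numerators and different at-risk sets.

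**Conclusion.** The point holds in limited form. As written, the concentration and antibody summaries pool subjects first exposed in 205MS303 with subjects exposed before, and nothing requires them to be shown apart.

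For concentrations, the consequence is confined to Week 0 and possibly Week 144. The Week 0 pooled mean is about 0.50 of steady-state trough against 0 and 1.00, given an equal split and no dosing gap, and the contrast falls towards nil as the gap approaches 6 months. The Week 144 mean lies between about 0.75 and 1.00 of steady state on planned numbers without dropout. At Week 12 the pooled mean is within about 1–7% of both groups under the assumed half-lives.

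For antibodies, the overall figure cannot separate those present at entry from those formed in 205MS303. The size cannot be known from the document. It is nil with no carried-in positivity, and carried-in subjects make up 9–63% of positives under the assumed 2–10%. The change is worth making because it serves stated secondary objectives at almost no cost.

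**What to change.** In Section 16.4.5:

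1. Summarise concentrations by visit, and ADA and NAb by time period and overall, within three groups: prior Avonex, prior DAC HYP in 205MS301, and entrants from 205MS203 or 205MS302.
2. Report subjects ADA-positive at Week 0 or Entry on a separate prevalence line, and count newly positive subjects among those negative at entry. Any count from first-ever DAC HYP under the Section 16.4.4 baseline can stand alongside, labelled as such.
3. Use the prior-Avonex column as the estimate for first exposure by prefilled syringe.

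The entry samples are already in the schedule (Week 0, and Week 144 for new entrants), so no procedure is added. The cost is wording, extra table columns and smaller denominators per column, so less precise estimates within each group.

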16.5. Interim Analyses

No formal interim analyses are planned for this study. However, analyses may be performed prior to the end of the study at the discretion of the Sponsor.

16.6. Sample Size Considerations

There is no formal sample size calculation. The number of subjects in this study is determined by the number of subjects who completed Study 205MS301, Study 205MS203, or Study 205MS302.

CONFIDENTIAL

The information contained herein may not be used, disclosed, or published without the written consent of Biogen MA Inc.

17. ETHICAL REQUIREMENTS

Biogen and the Investigator must comply with all instructions, regulations, and agreements in this protocol and applicable International Council for Harmonisation (ICH) and Good Clinical Practice (GCP) guidelines and conduct the study according to local regulations.

17.1. Declaration of Helsinki

The Investigator and Biogen must adhere to the principles set forth by the Declaration of Helsinki dated October 2008.

17.2. Ethics Committee

The Investigator must obtain ethics committee approval of the protocol, ICF, and other required study documents prior to starting the study. The Sponsor may submit documents on behalf of the study sites in countries other than the US as applicable.

If the Investigator makes any changes to the ICF, Biogen must approve the changes before the ICF is submitted to the ethics committee. A copy of the approved ICF must be provided to Biogen. After approval, the ICF must not be altered without the agreement of the relevant ethics committee and Biogen.

It is the responsibility of the Principal Investigator(s) to ensure that all aspects of institutional review are conducted in accordance with current governmental regulations.

Biogen must receive a letter documenting ethics committee approval, which specifically identifies the protocol, protocol number, and ICF, prior to the initiation of the study. Protocol amendments will be subject to the same requirements as the original protocol.

A progress report must be submitted to the ethics committee at required intervals and not less than annually.

At the completion or termination of the study, the study site must submit a close-out letter to the ethics committee and Biogen.

17.3. Subject Information and Consent

Prior to performing any study-related activities under this protocol, including Baseline/Entry Visit tests and assessments, written informed consent with the approved ICF must be obtained from the subject or subject's legally authorized representative, as applicable, in accordance with local practice and regulations. Written informed consent must be obtained from all subjects participating in a clinical study conducted by Biogen.

The background of the proposed study, the procedures, the benefits and risks of the study, and that study participation is voluntary for the subject must be explained to the subject. The subject must be given sufficient time to consider whether to participate in the study.

A copy of the ICF, signed and dated by the subject, must be given to the subject. Confirmation of a subject's informed consent must also be documented in the subject's medical record prior to any testing under this protocol, including Baseline/Entry Visit tests and assessments.

CONFIDENTIAL

The information contained herein may not be used, disclosed, or published without the written consent of
Biogen MA Inc.

Each consent form should contain an authorization allowing the Principal Investigator(s) and Biogen to use and disclose PHI (i.e., subject-identifiable health information) in compliance with local law.

The signed consent form will be retained with the study records.

17.4. Subject Data Protection

Prior to any testing under this protocol, including Baseline/Entry Visit tests and assessments, candidates must also provide all authorizations required by local law (e.g., PHI authorization in North America).

The subject will not be identified by name in the CRF or in any study reports and these reports will be used for research purposes only. Biogen, its partner(s) and designee(s), ethics committees, and various government health agencies may inspect the records of this study. Every effort will be made to keep the subject's personal medical data confidential.

17.5. Compensation for Injury

Biogen maintains appropriate insurance coverage for clinical trials and will follow applicable local compensation laws.

17.6. Conflict of Interest

The Investigators should address any potential conflicts of interest (e.g., financial interest in the Sponsor) with the subject before the subject makes a decision to participate in the study.

17.7. Registration of Study and Disclosure of Study Results

Biogen will register the study and post study results regardless of outcome on a publicly accessible website in accordance with the applicable laws and regulations.

CONFIDENTIAL

The information contained herein may not be used, disclosed, or published without the written consent of Biogen MA Inc.

18. ADMINISTRATIVE PROCEDURES

18.1. Study Site Initiation

The Investigator must not enroll any subjects prior to completion of a study initiation visit, conducted by Biogen or designee. This initiation visit will include a detailed review of the protocol and study procedures.

18.2. Quality Assurance

During and/or after completion of the study, quality assurance officers named by Biogen or the regulatory authorities may wish to perform on-site audits. The Investigator will be expected to cooperate with any audit and to provide assistance and documentation (including source data) as requested.

18.3. Monitoring of the Study

The Principal Investigator(s) must permit study-related monitoring by providing direct access to source data and to the subjects' medical histories.

The Clinical Monitor(s) will visit the Investigator(s) at regular intervals during the course of the study and after the study has completed, as appropriate.

During these visits, CRFs and supporting documentation related to the study will be reviewed and any discrepancies or omissions will be resolved.

The monitoring visits must be conducted according to the applicable ICH and GCP guidelines to ensure protocol adherence, quality of data, study treatment accountability, compliance with regulatory requirements, and continued adequacy of the study site and its facilities.

